assessing the feasibility rate. To establish the decision rule we will compute the sample feasibility rate (i.e., the number of patients who could be successfully treated divided by the total number of evaluable patients, which we expect to range from 25 to 30) and form an 80% 2-sided Clopper-Pearson exact confidence interval. If the lower bound of this exact confidence interval is greater than 66% then we will declare this procedure feasible. Namely, we will test the hypotheses $H_0: \theta \leq 0.66$ vs. $H_1: \theta > 0.66$ at $\alpha=0.05$, where θ denotes the feasibility rate. The test statistic will be the lower bound of the 90% 2-sided Clopper-Pearson exact confidence interval for binomial trials. Equivalently, this test statistic can be written as $\text{Beta}(0.05, X, N+1-X)$, i.e., the 5th-percentile of the beta distribution with two parameters X and $N+1-X$, where X and N denote the number of successes and the total sample size (expected to be from 25 to 30), respectively. When the sample size is as small as 25, the power of rejecting the null hypothesis is 61%, 84% and 97% when the true feasibility rate is 0.80, 0.85 and 0.90, respectively. When the sample size is as large as 30, such power becomes 61%, 85% and 97%. Since we expect the feasibility rate to be around 0.85, the sample size is sufficiently large. We expect to finish the recruitment in 4 years.

For protective purposes we will implement a stopping rule to prevent excessive rate of pneumothorax or hospitalization (related to the proposed procedure). If 6 or more events (i.e., procedure-related pneumothorax or hospitalization) among the first 30 patients, or 11 or more events among the total 55 patients we plan to enroll are observed, we will halt the trial to thoroughly investigate such events. This sequential stopping rule has the following probability of halting the trial:

True event probability	0.05	0.08	0.10	0.15	0.20	0.25	0.30
Probability of halting the trial	0.003	0.030	0.081	0.342	0.679	0.900	0.978

In addition, a second stopping rule will be implemented if a maximum of two device migrates to a critical organ, such as the heart or brain, or if one device-related death is observed.

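### Power is given only at 25 and 30 evaluable patients, but exact-test power dips below both values at some sizes in between, so 84–85% is not delivered across the planned range

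*Combined protocol and SAP*

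**What the plan says.** All of the following is in section 14.0 of the combined protocol and SAP.

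- **Denominator.** The feasibility rate is the number successfully treated divided by "the total number of evaluable patients, which we expect to range from 25 to 30". Thirty patients are enrolled upfront, and at least 25 are expected to be evaluable. The 25-to-30 range is repeated where the test statistic is defined.
- **Decision rule.** The plan will "form an 80% 2-sided Clopper-Pearson exact confidence interval", and then: "If the lower bound of this exact confidence interval is greater than 66% then we will declare this procedure feasible".
- **The same rule, stated differently.** The hypotheses are tested at a one-sided alpha of 0.05, and "The test statistic will be the lower bound of the 90% 2-sided Clopper-Pearson exact confidence interval for binomial trials".
- **Power.** At N=25, "the power of rejecting the null hypothesis is 61%, 84% and 97% when the true feasibility rate is 0.80, 0.85 and 0.90, respectively". For the other end: "When the sample size is as large as 30, such power becomes 61%, 85% and 97" (per cent).
- **Conclusion.** "Since we expect the feasibility rate to be around 0.85, the sample size is sufficiently large".

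No power is given for N=26, 27, 28 or 29, and the section does not mention that power may vary irregularly between the two sizes shown. It also says that the first and second sets of 25 evaluable patients are analysed separately.

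**The concern.** The final N is not under the sponsor's control; it depends on how many of the 30 turn out evaluable. Giving nearly identical power at the smallest and largest N invites the reader to take about 84–85% as holding throughout. For an exact binomial test that does not follow. The pass mark is a whole number of successes. Over some stretches of N, each extra patient raises the pass mark by one, so the test becomes stricter and power falls. At other steps the pass mark stays put and power jumps up.

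The conclusion that the sample is adequate rests on these two points at a true rate of 0.85. If power is lower at several of the sizes that may occur, the plan overstates the chance of declaring a truly feasible procedure feasible. The pass mark for those sizes is also not written down anywhere.

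**Working it through.** **Inputs (section 14.0).** Threshold 0.66; N from 25 to 30; true rates 0.80, 0.85 and 0.90; lower confidence bound from either an 80% two-sided interval (one-sided tail a = 0.10) or a 90% two-sided interval (a = 0.05).

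**Formulas.** The Clopper-Pearson lower bound is the a-quantile of the Beta(X, N+1−X) distribution. The critical value c is the smallest X whose lower bound exceeds 0.66. Power at rate p is P(X ≥ c) for X ~ Binomial(N, p). Exact type I error is the same probability at p = 0.66.

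**Step 1: reproduce the plan's figures.** With a = 0.10:

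- N=25: X=20 has lower bound 0.6603, so c=20. Power is 61.7 / 83.8 / 96.7%, against the stated 61 / 84 / 97%.
- N=30: X=24 has lower bound 0.6753, so c=24. Power is 60.7 / 84.7 / 97.4%, against the stated 61 / 85 / 97%.

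All six agree to within one point. With a = 0.05 they do not: N=25 (c=21) gives 42.1 / 68.2 / 90.2%, and N=30 (c=25) gives 42.8 / 71.1 / 92.7%. The quoted power therefore belongs to the 80% interval rule.

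**Step 2: fill in the range under the 80% interval rule.**

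| N | c | Type I error | Power at 0.80 | Power at 0.85 | Power at 0.90 |
|---|---|---|---|---|---|
| 25 | 20 | 0.099 | 61.7% | 83.8% | 96.7% |
| 26 | 21 | 0.079 | 57.7% | 81.5% | 96.0% |
| 27 | 22 | 0.063 | 53.9% | 79.0% | 95.3% |
| 28 | 23 | 0.049 | 50.1% | 76.5% | 94.5% |
| 29 | 23 | 0.090 | 64.3% | 86.7% | 97.8% |
| 30 | 24 | 0.073 | 60.7% | 84.7% | 97.4% |

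From N=25 to N=28 the pass mark rises by one with each patient and power falls. At N=29 the pass mark stays at 23 and power recovers. At 0.85 the low point, N=28, is 83.8 − 76.5 = 7.3 points below N=25 and 84.7 − 76.5 = 8.2 points below N=30. At 0.80 the low is 50.1%, 10.6 points below the lower end point (60.7%). At 0.90 the loss at N=28 is 2.2 to 2.9 points.

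**Step 3: the same under the 90% interval rule (alpha 0.05).**

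| N | c | Type I error | Power at 0.80 | Power at 0.85 | Power at 0.90 |
|---|---|---|---|---|---|
| 25 | 21 | 0.040 | 42.1% | 68.2% | 90.2% |
| 26 | 22 | 0.031 | 38.3% | 65.0% | 88.8% |
| 27 | 23 | 0.023 | 34.8% | 61.9% | 87.3% |
| 28 | 23 | 0.049 | 50.1% | 76.5% | 94.5% |
| 29 | 24 | 0.039 | 46.3% | 73.8% | 93.6% |
| 30 | 25 | 0.030 | 42.8% | 71.1% | 92.7% |

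Here N=26 and N=27 fall below both end points, and N=28 has the highest power in the range. The dip at 0.85 is 68.2 − 61.9 = 6.3 points below N=25 and 71.1 − 61.9 = 9.2 points below N=30.

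**The case against.** **No quoted number is wrong.** This stands. The six figures reproduce under the 80% interval rule, and the section labels them by sample size without calling them bounds. The defect is incomplete reporting. It still matters, because the adequacy of the sample is argued from those two points alone.

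**The average loss is small.** This also stands. With equal weight on N=25 to 30 (an assumption; the plan gives no distribution for N), mean power at 0.85 under the 80% rule is (83.8 + 81.5 + 79.0 + 76.5 + 86.7 + 84.7) / 6 = 82.0%, some 2 to 3 points under the quoted values. N=26 is only 2 to 3 points low, and N=29 is better than either end. That is a reason to report the range rather than the minimum alone.

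**N is really 25.** Section 14.0 refers to two sets of 25, section 4.1 speaks of success in the first 25 patients, and section 1.0 describes an extension of 25. At exactly N=25 no dip arises. But section 14.0 twice puts the denominator at 25 to 30 for the cohort of 30 enrolled upfront, so the point holds for that cohort. It does not extend to a set analysed at exactly 25.

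**Settling the interval conflict would cure this.** Only if every N is then tabulated. A dip exists under either rule, so correcting the interval and again quoting only N=25 and N=30 would leave the gap.

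Two stronger readings are tempting. A reader might infer that N=26 to 28 is low under both rules; under the 90% rule N=28 is the best size in the range. A reader might also set the 61.9% minimum under the 90% rule against the stated 84% and blame the whole difference on the dip. Under that rule power is already 68.2% at N=25, so about 16 of the 22 points come from the 80%/90% conflict, which is a separate matter.

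**Conclusion.** The point holds as incomplete power reporting for the upfront cohort. Under the rule that generated the quoted figures, three of the six possible sizes (N=26, 27 and 28) have power at 0.85 below both quoted values, and two of them (N=27 and 28) are below 80%. Power at 0.85 ranges from 76.5% to 86.7% under the 80% interval, and from 61.9% to 76.5% under the 90% interval. The effect is largest at a true rate of 0.80 and small at 0.90.

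This rests on the threshold of 0.66, on every evaluable patient counting in the denominator, and on independent patients with a common success rate, as the plan's own binomial calculation assumes. A reader might infer that the trial must be enlarged. The documents do not support that: they set no minimum power, and adding one patient can lower power as easily as raise it.

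**What to change.** 1. Settle first which interval governs the decision, 80% or 90%, and make the stated alpha agree with it.
2. Replace the two quoted power points with a six-row table for N=25 to 30 giving the critical X, the exact type I error, and the power at 0.80, 0.85 and 0.90. The matching table above can be used as it stands.
3. In place of 84–85%, state the range at 0.85: 76.5–86.7% for the 80% interval, or 61.9–76.5% for the 90% interval. Reword the sentence on adequacy to match.
4. Say that this applies to the cohort of 30 enrolled upfront. For any set analysed at exactly 25 patients, give the N=25 power only.

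The cost is one small table and one reworded sentence. Neither the sample size nor the 66% threshold needs to change for this point. The only downside is a less favourable stated power; the gain is that the pass mark is fixed in advance for whichever N occurs.

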evaluable patients, two patients experienced a pneumothorax (Grade 2), one patient had anesthesia-related cardiac arrest (Grade 4), two patients experienced cough (Grade 2) and one patient had dyspnea (Grade 2) after the bronchoscopy, one patient had lung infection (Grade 3), and two patients had migration of one fiducial marker each that did not impact the ability to track the tumor during radiation treatments.[38, 51.] The use of Calypso transponders holds the potential for a great benefit of real-time tumor position information without the use of ionizing radiation from additional intrafraction imaging. Calypso transponders have been routinely used in our department as a motion monitoring system for prostate RT for about 5 years. The entire system including 4D console, electromagnetic array, tracking station and optical system is in place on a linear accelerator that is equipped for lung RT and on-board kV imaging.

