8. Removal of the LG while maintaining the EWC in place
9. Confirmation with rEBUS that the EWC is at the lesion of interest
10. Placement of 3 Calypso beacon transponders in or near the lesion of interest under fluoroscopic guidance
11. Fluoroscopic confirmation of placement
12. Removal of EWC
13. Final bronchoscopic evaluation of the airways
14. Emergence from anesthesia with standard post-procedural care, including a portable CXR

During the procedure, all care will be taken to reduce the risk of adverse events for the placement of the fiducials. The use of Olympus rEBUS and fluoroscopy, in addition to the SuperDimension ENB system, will further reduce the risk of adverse events, including pneumothorax. As previously noted, the risk of adverse events during the placement of fiducials is very low, with the majority of the risk associated with anesthesia. [37, 46-48, 50].

There is an inherent increased risk for these patients since they will have to undergo a bronchoscopy for the placement of fiducials as part of the radiation therapy, unlike patients who are undergoing radiation therapy without fiducial placement. Since the majority of these patients have many medical comorbidities and have been deemed non-operable, a complete pre-operative assessment will be performed by either the Thoracic Surgery or Pulmonology service, with standard anesthesia evaluation done during pre-surgical testing, to confirm that the patient is an acceptable risk for anesthesia. This may include formal cardiac and pulmonary studies, as well as appropriate specialty consultations, including internal

medicine, geriatrics or cardiology, at the discretion of the treating physician. If it is determined that the risk of anesthesia is too great, the patient will not be eligible for this study.

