- c. Only serious adverse events that are at least possibly related to the investigational product will be reported as the radiation therapy is considered standard of care.

3. Definition of an Unexpected Adverse Event

- a. An Unexpected AE is an experience not previously reported (in nature, severity, or incidence) in the current Investigator's Brochure or general investigational plan.

Evaluation of SAE:

Review of the patient record including the treatment dosimetry will be undertaken by the principal investigator. The principal investigator may decide to continue the protocol without modification, discontinue the study altogether, or to modify the protocol prior to enrolling more patients pending the results of the review. However, if the SAE meets the criteria for the stopping rule, as defined in Section 14.0, the trial will be stopped.

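### The only death trigger in the stopping rules is limited to device-related deaths, a term left undefined, so a death from bronchoscopy or anesthesia does not clearly stop the trial

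*Combined protocol and SAP*

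**What the plan says.** Section 14.0 contains two stopping rules.

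- **Event rule.** The limit at the first look reads "If 6 or more events (i.e., procedure-related pneumothorax or hospitalization) among the first 30 patients". A further limit applies to the whole planned enrollment: "or 11 or more events among the total 55 patients we plan to enroll are observed". Reaching either one halts the trial so that the events can be investigated. A table introduced by "This sequential stopping rule has the following probability of halting the trial" gives the halting probability for true event rates from 0.05 to 0.30. Death is not named as an event.
- **Second rule.** This covers device migration to a critical organ, "or if one device-related death is observed". The documents do not define device-related.

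Four other places bear on how these rules are read.

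- Section 11.0 groups the expected toxicities under separate headings for anesthesia, flexible bronchoscopy, implantation or markers, and radiation. After a serious adverse event, "The principal investigator may decide to continue the protocol without modification", or may modify or discontinue the study. A stop is compulsory only when a Section 14.0 rule is met.
- Section 17.0 (side effects) names anesthesia risk among the effects particular to implanting the markers.
- Section 5.0 calls the risk of placing the markers very low, "with the majority of the risk associated with anesthesia".
- Sections 3.1.1 and 3.2 report one grade 4 anesthesia-related cardiac arrest among the 48 patients of the cited interim series. They list no death.

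**The concern.** The two rules attribute events differently. The first looks to the procedure but does not name death; the second names death but looks to the device. A death caused by the bronchoscopy or its anesthesia falls between them unless it is read as device-related. That matters because patients undergo this bronchoscopy for marker placement, most of them are described as inoperable with many comorbidities, and the protocol itself locates most of the placement risk in anesthesia.

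The plan treats one device-related death as enough to trigger the rule. How a single case is attributed therefore decides between a compulsory stop and a discretionary review, and the plan leaves that attribution open.

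**Working it through.** **1. The plan's own table.** Inputs are the limits and the table in Section 14.0. With X30 the events among the first 30 patients and X25 the events among the next 25, at a true event probability p:

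P(halt) = P(X30 ≥ 6) + Σ over x = 0 to 5 of P(X30 = x) · P(X25 ≥ 11 − x).

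| True rate | Stated | Exact |
|---|---|---|
| 0.05 | 0.003 | 0.0033 |
| 0.08 | 0.030 | 0.0305 |
| 0.10 | 0.081 | 0.0789 |
| 0.15 | 0.342 | 0.3388 |
| 0.20 | 0.679 | 0.6780 |
| 0.25 | 0.900 | 0.8978 |
| 0.30 | 0.978 | 0.9788 |

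At p = 0.10, for example, the first look contributes 0.0732 and the second 0.0057, giving 0.0789. The largest difference from the stated values is about 0.003, so the table is sound. It describes the event rule only and gives no operating characteristics for the death trigger.

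**2. Tracing one patient through the rules.**

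| Outcome | Device-related excludes anesthesia and bronchoscopy | Device-related includes them |
|---|---|---|
| Death from anesthesia or bronchoscopy, no pneumothorax, no admission | 0 events; death trigger not met | Death trigger met |
| The same death after a procedure-related pneumothorax or admission | 1 event toward 6 or 11; death trigger not met | Death trigger met |
| Non-fatal arrest with admission | 1 event | 1 event |

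In the first column neither death triggers a rule by itself, unless enough other events have already accrued for it to be the sixth or eleventh.

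**3. Which column applies.** The separate headings in Section 11.0, and the use of both procedure-related and device-related within Section 14.0, favor the first. Section 17.0 favors the second. Nothing in the documents settles it.

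**4. Size.** The observed arrest rate is 1/48 = 2.1%, with an exact (Clopper-Pearson) 95% interval of 0.05% to 11.1%. That is a rate of arrest, not of death, and no fatality rate is given. For illustration only, assume a per-patient probability q of a bronchoscopy or anesthesia death. The chance of at least one in n patients is 1 − (1 − q)^n. The last column is the chance that the event rule halts on such deaths alone if every one is also counted as a hospitalization, using the formula in step 1 with p = q.

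| Assumed q | At least one in 30 | At least one in 55 | Event rule halts on these deaths alone |
|---|---|---|---|
| 0.5% | 14% | 24% | about 8 × 10⁻⁹ |
| 1% | 26% | 42% | about 5 × 10⁻⁷ |
| 2% | 45% | 67% | about 3 × 10⁻⁵ |

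The event rule therefore cannot stand in for a death trigger, even when every such death is scored.

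**The case against.** A reader might infer that a procedural death scores nothing, or that the scoring is reversed because a survivor of an arrest who is admitted counts while a patient who dies does not. The documents do not support that as a general statement. A death preceded by a procedure-related admission or pneumothorax scores one event, and the contrast holds only for a death with neither that is also judged not device-related. Section 17.0 allows the reading under which an anesthesia death during implantation meets the death trigger at once.

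Nor is the investigator the only safeguard. Section 16.2 describes institutional monitoring committees, Section 17.2 makes death a reportable serious adverse event, and Sections 5.0 and 6.2 keep out patients for whom anesthesia is too risky. It can also be argued that limiting the one-death trigger to the device under study is a legitimate choice where bronchoscopic localization is in routine use.

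These points narrow the concern without removing it. The other oversight is discretionary: Section 11.0 compels a stop only through Section 14.0. Reporting is itself unclear, because Section 11.0 limits it to serious events at least possibly related to the investigational product. If the narrow trigger is deliberate, the plan should say so and define the term.

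The single arrest cannot be turned into a probability of death. It was graded 4, the series lists no death, and any fatal share would be supplied from outside the documents.

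**Conclusion.** The point holds as a gap in wording with a safety consequence. A death from bronchoscopy or anesthesia does not clearly trigger either stopping rule. On the narrower reading it scores at most one event toward 6/30 or 11/55, and none without pneumothorax or admission. The conclusion rests on the text and not on an event rate: the plan's threshold is one death, so the attribution of one patient decides the outcome. The step 4 probabilities are conditional on assumed rates and are not estimates for this trial. The halting table is correct, and the primary analysis is unaffected. This is a cheap improvement to safety monitoring rather than an error in the design calculations.

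**What to change.** In Section 14.0, reword the death trigger to: *one death related to the device or to its placement (implantation, bronchoscopy or anesthesia)*. Then reconcile Sections 11.0, 14.0 and 17.0 so that attribution to device, procedure and anesthesia is used consistently. State also whether meeting a rule means a halt for investigation, as the event rule in Section 14.0 has it, or that the trial is stopped, as Section 11.0 has it.

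Death need not be added to the 6/30 and 11/55 count, because the first placement-related death would already meet the reworded trigger. Those limits and the halting table stay unchanged.

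The cost is a sentence or two of amendment and the possibility that one placement-related death halts accrual for review. If the Section 11.0 wording is kept, that consequence would be a stop, which is why the two sections need to be settled together.
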